6.2.3.4 Diagnostic confidence

The BRs will record in the eCRF his/her confidence in diagnosis for each subject for the combined unenhanced and gadobutrol-enhanced MR image sets, and the combined unenhanced and gadoterate-enhanced MR image sets separately.

Diagnostic confidence will be evaluated to determine the level of certainty that the BRs assign to a diagnosis. This is defined as the degree of confidence that the information on the images represents the true and complete clinical picture of a subject. The degree of confidence will be rated on a 4-point scale:

- 1 = Not confident
- 2 = Somewhat confident
- 3 = Confident
- 4 =Very confident

When the BR chooses "not assessable" for diagnosis, by definition the confidence level is 1 (not confident).

Frequency tables for confidence responses (1-4) for subjects will be constructed for combined unenhanced and gadoterate-enhanced MRI, and combined unenhanced and gadobutrol-enhanced MRI. Descriptive statistics for the combined unenhanced/gadobutrol-enhanced MRI and the combined unenhanced/gadoterate-enhanced MRI will be generated. The 95% CIs for the differences based on a t-distribution will be generated.

6.2.3.5 Image quality

The BRs will evaluate the relative image quality of the gadobutrol-enhanced T1w MR images and the gadoterate-enhanced T1w MR images in a third read session different from the 2 sessions mentioned in Section 6.2.1. The assessment will be based on the overall subjective interpretation of the degree of contrast enhancement, border delineation, and internal morphology. These images will be presented in a paired fashion in a separate reading session. The gadobutrol and gadoterate images will be randomly assigned to either the left (image L) or right (image R) positions.

Image quality will be compared on a 5-point scale:

- 1 =Image R is worse
- 2 =Image R is slightly worse
- 3 =Image R is same
- 4 =Image R is slightly better
- 5 =Image R is better

After the data are unblinded, the above codes will be translated into the following scale:

- -2 = Gadobutrol image set is worse
- -1 = Gadobutrol image set is slightly worse
- 0 = Image sets are the same
- 1 = Gadobutrol image set is slightly better
- 2 = Gadobutrol image set is better

Frequency tables and descriptive statistics will be generated on these values and the combined values (Gadobutrol is better/slightly better) and (Gadobutrol is worse/slightly worse) yielding a 3 point scale Gadobutrol is better, same, or worse. The relative image qualities will be tested for equality using a Wilcoxon signed-rank test.

6.2.4 MRI field strengh

Field strength used in the MRI scan (1.5 Tesla, 3.0 Tesla) will be summarized for total subjects in FAS and PPS.

6.3 Pharmacokinetics/pharmacodynamics

Not applicable.

6.4 Safety

6.4.1 Baseline findings

A baseline finding is defined as any untoward medical condition in a study subject who has signed the informed consent form but has not received the first dose of the study drug.

Conditions that started before signature of informed consent and for which no symptoms or treatment are present until the first administration of study drug (e.g., seasonal allergy without acute complaints) are recorded as medical/surgical history.

Conditions (e.g., abnormal physical examination findings, symptoms, diseases, or laboratory test results) present between signature of informed consent and the first administration of study drug will be documented as baseline findings and analyzed as **pretreatment AEs**.

Baseline findings will be regarded as serious if they meet the criteria used for defining SAEs and they will be reported on the SAE form.

6.4.2 Adverse events

The AE monitoring will begin with the administration of the contrast agent in Study Period 1 and will end after the last follow-up evaluation. Safety will be assessed using data from TEAEs. A **TEAE** is defined as any AE that increases in intensity or that is newly developed during the TE period for Study Period 1 or Study Period 2. If an AE starts (or increases in severity) during the TE period for a specific study period, this AE will be attributed to the treatment the subject received during the study period.

Page: 27 of 29:

A **post-treatment AE** is defined as an AE that increase in severity or that is newly developed in post-treatment period as defined in Section 6.

The AEs are to be coded using the current MedDRA version.

Frequencies of AEs will be tabulated by contrast agent and the proportions of subjects exhibiting each AE will be displayed.

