5.1 Design overview

This study is a Phase 4, multicenter, controlled, cross-over study with corresponding blinded image evaluations in male and female patients at least 18 years of age, who are referred for a contrast-enhanced MRI of the CNS based on a known or highly suspected lesion of the CNS.

Patients will undergo an unenhanced and contrast-enhanced MRI of the CNS using gadoterate at the standard dose of 0.1 mmol/kg BW. If the investigator does not identify an enhancing lesion of the CNS, then this patient will be considered a screening failure. If an enhancing lesion is identified, then the patient will undergo a second unenhanced and contrast-enhanced MRI of the CNS using gadobutrol at a dose of 0.075 mmol/kg BW.

Safety will be assessed from the first administration of gadoterate through 24 hours after the second administration of gadobutrol. Adverse events will be collected from the signing of informed consent through the end of the follow-up period. Serious adverse events (SAEs) will be followed through resolution. Patients who receive only the first MRI scan (considered screening failures) will be followed for SAEs only.

Gadobutrol will be administered at the dose of 0.075 mmol/kg body weight by single IV injection at a rate of 2 mL/sec, followed by 20-mL 0.9% saline flush at the same rate. Gadoterate will be administered at the approved standard dose of 0.1 mmol/kg body weight by single IV injection at 2 mL/sec, followed by 20-mL 0.9% saline flush at the same rate. The 2 injections will be separated by at least 24 hours, but not more than 15 days.

During the course of the study, 2 MRIs will be obtained from each patient as follows: before the administration of each of the contrast agent (unenhanced MRI) consisting of steady-state sequences (T1w, T2w, and FLAIR), following the gadoterate injection (gadoterate-enhanced MRI) consisting of steady-state sequences T1; and following the gadobutrol injection (gadobutrol-enhanced MRI) consisting of steady-state sequences (T1w).

The unenhanced MR image set, combined unenhanced and gadobutrol-enhanced MR image sets, and the unenhanced and combined unenhanced and gadoterate-enhanced MR image sets will be evaluated by 3 independent blinded readers. The blinded readers will also evaluate the

26 MAR 2019 Version no. 2.0 Page: 15 of 60

gadobutrol-enhanced T1w images compared to the gadoterate-enhanced T1w images in a paired read for image quality.

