9.2 Study periods

9.2.1 Baseline study period 1

Baseline is the up to 72 hour period from signing informed consent to administration of gadoterate (including saline flush).

Prior to administration of gadoterate the following will be performed: placement of IV injection line, urine pregnancy test (in women of child bearing potential the date and time of the pregnancy test sample and the result of the pregnancy test will be recorded in the eCRF). Results of the pregnancy test must be negative prior to the administration of any contrast agent.

The IV injection line will consist of a large bore indwelling catheter (at least 18 gauge) preferably placed in an antecubital vein. The location of the IV injection line must be documented in the eCRF.

9.2.2 Study period 1

The administration of gadoterate is study period 1 and the administration of the gadobutrol is study period 2.

The following procedures will be performed during study period 1:

- 1. An unenhanced MRI of the brain will be performed according to the standards of the institution.
- 2. The appropriate volume corresponding to 0.1 mmol/kg of gadoterate will be administered IV as a bolus injection at the rate of 2 mL/sec using a power injector via a peripheral vein (the antecubital vein is preferred) followed by a 20-mL 0.9% saline flush using a power injector at the same flow rate. The dose and volume of the contrast agent will be recorded.
- 3. AE monitoring will begin at baseline. All TEAEs will be monitored for 24 hours after the administration of each contrast agent. However, if no enhancing lesion is identified in the first imaging study, the patient will not be included in the safety database and only SAEs for that patient would be reported.
- 4. Conventional steady-state contrast-enhanced imaging with a T1w sequence according to the parameters listed in Section 10.2.1.2 will start 4 to 10 minutes following the injection of the contrast agent.
- 5. The patient will be asked about his/her physical condition. Any clinically significant changes in the patient's physical condition from the baseline values are to be recorded in the eCRF, and the TEAE section is to be completed accordingly.

26 MAR 2019 Version no. 2.0 Page: 27 of 60

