10.3 Pharmacokinetics

Not applicable.

- 10.4 Safety
- **10.4.1** Adverse events
- 10.4.1.1 Definitions

Definition of adverse event (AE) and treatment emergent AEs

In this study, adverse events (AEs), defined as any untoward medical occurrence (i.e. any unfavorable and unintended sign [including abnormal laboratory findings], symptom or disease) in a patient or clinical investigation patient after signing informed consent will be recorded.

A treatment emergent AE is defined as any AE that is reported after the patient has received at least one dose of study drug. Therefore, a TEAE may or may not be temporally or causally associated with the use of a medicinal (investigational) product.

Pathology identified on the MRI will not be considered a TEAE.

26 MAR 2019 Version no. 2.0 Page: 35 of 60

A surgical procedure that was planned prior to the start of the study by any physician treating the patient should not be recorded as a TEAE (however, the condition for which the surgery is required may be a TEAE).

In the following differentiation between medical history and TEAEs, the term "condition" may include abnormal e.g. physical examination findings, symptoms, diseases, laboratory results, ECG.

- Conditions that started before signing of informed consent and for which no symptoms or treatment are present until signing of informed consent are recorded as medical history (e.g. seasonal allergy without acute complaints).
- Conditions that started before signing of informed consent and for which symptoms or treatment are present after signing of informed consent, at *unchanged intensity*, are recorded as medical history (e.g. allergic pollinosis).
- Conditions that started or deteriorated after signing of informed consent will be documented as adverse events. This includes intercurrent illnesses.

Definition of serious AE (SAE) and treatment emergent serious (TESAE)

A SAE is classified as any untoward medical occurrence that, at any dose, meets any of the following criteria (a - f) and a TESAE is any SAE that is reported after the patient has received at least one dose of study drug.

The criteria for both an SAE and a TESAE are:

- a. Results in death
- b. Is life-threatening

The term 'life-threatening' in the definition refers to an event in which the patient was at risk of death at the time of the event, it does not refer to an event which hypothetically might have caused death if it were more severe.

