10.4.1.3 Assessments and documentation of adverse events

The investigator must record on the respective CRF pages all adverse events occurring in the period between the signing of the informed consent and the end of the follow-up phase; all SAEs/TESAEs must be followed to resolution. After the end of the follow-up phase there is no requirement to actively collect TEAEs including deaths. The type of information that should be assessed and recorded by the investigator for each TEAE is listed in Section 10.4.1.2.

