- The **post-treatment period** is the period after the last date of TE period for Treatment Period 2 to the date of the last study record in the clinical database or the period between the end of TE period for Treatment Period 1 and the start of TE period for Treatment Period 2.
- The baseline value is defined as the most recent nonmissing assessment (scheduled or unscheduled) collected up to 72 hours prior to first administration of study drugs in the whole study. This will include values collected at baseline visit with regard to the gadoterate scan but before signing informed consent.

6.1 **Population Characteristics**

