6.4.2.1 Overview of AEs

The number and percentage of subjects experiencing AEs will be summarized. Overall summary tables will be provided for all AEs, TEAEs and pretreatment AEs with following categories:

- Any such AEs
- Drug-related AEs
- AEs related to procedures required by the protocol
- AEs by intensity (mild, moderate, severe)
- Drug-related AEs by intensity
- Serious AEs (SAEs)
- Drug-related SAEs
- SAEs related to procedures required by the protocol
- AEs leading to discontinuation of study drug
- SAEs leading to discontinuation of study drug
- AEs leading to death.

The overall summary table will also be presented on AEs of subjects only receiving gadoterate but not included in the SAF.

The number and percentage of subjects with TEAEs will be summarized for the following:

- TEAEs and treatment-emergent SAEs (TESAEs) by SOC and PT
- Drug-related TEAEs and TESAEs by SOC and PT
- Nonserious TEAE by SOC and PT
- TEAEs and TESAEs resulting in discontinuation of study drug by SOC and PT
- TEAEs and TESAEs by maximum intensity, SOC, and PT
- Drug-related TEAEs and TESAEs by maximum intensity, SOC, and PT
- TEAEs and TESAEs by worst outcome, SOC, and PT
- Drug-related TEAEs and TESAEs by worst outcome, SOC, and PT

Common TEAEs, TESAEs, drug-related TEAEs, and drug-related TESAEs with frequency $\geq 1\%$ by SOC and PT.

Tables will be sorted alphabetically by SOC and PT.

Subject listings of all AEs as well as subset listings of AEs leading to death and AEs resulting in discontinuation of study drug will be created.

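### Adverse events starting after the 24 ± 4 h window following gadoterate and before gadobutrol are treatment-emergent under the protocol but post-treatment under the SAP, and appear in none of the SOC/PT tables listed in SAP 6.4.2.1

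*SAP*

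**What the plan says.** **Protocol.** Section 10.4.1.1 gives the definition: "A treatment emergent AE is defined as any AE that is reported after the patient has received at least one dose of study drug". For serious events, "a TESAE is any SAE that is reported after the patient has received at least one dose of study drug". Neither definition has a closing time or a window per agent. Section 5.1 describes one continuous span: "Safety will be assessed from the first administration of gadoterate through 24 hours after the second administration of gadobutrol". SAP 3.1 repeats this. Section 10.4.1.3 has the investigator record "all adverse events occurring in the period between the signing of the informed consent and the end of the follow-up phase". Section 9.2.2, however, states: "All TEAEs will be monitored for 24 hours after the administration of each contrast agent".

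**SAP.** Section 6 sets two treatment-emergent (TE) periods, each running from an injection to 24 ± 4 h later. Its post-treatment period is the time after the second TE period "or the period between the end of TE period for Treatment Period 1 and the start of TE period for Treatment Period 2". In section 6.4.2 a treatment-emergent event "is defined as any AE that increases in intensity or that is newly developed during the TE period for Study Period 1"; the same rule holds for the second period, and post-treatment AEs are a separate class. An AE is attributed to an agent only if it starts or worsens within a TE period.

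For output, section 6.4.2.1 states: "Overall summary tables will be provided for all AEs, TEAEs and pretreatment AEs with following categories". Every SOC/PT table it then lists is for TEAEs or TESAEs. Section 6.4.2 also has a general sentence planning frequencies of AEs, by contrast agent and for each AE, that is not limited to TEAEs.

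**The concern.** The injections may be up to 15 days apart. Events in most of a long interval must be recorded and lie inside the stated safety span, yet the SAP's definition removes them from the treatment-emergent class. Safety is a secondary objective, and Protocol 11.4.2.6 promises TEAE tabulations by agent, with a separate set for serious TEAEs. If the SAP is followed as written, TEAE and TESAE counts can only equal or fall below those given by the protocol's definition. They fall below as soon as one event starts in the gap and does not worsen after gadobutrol. A serious event there would be missing from every table of treatment-emergent serious events, and the change history in SAP section 7 does not tell the reader that the definition differs from Protocol 10.4.1.1.

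**Working it through.** The documents state no figure to reproduce. The check has two parts: following one event through both documents, and measuring the gap.

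**1. One event.** Take an SAE that starts on day 5 after gadoterate in a subject given gadobutrol on day 7, and that does not worsen after gadobutrol.

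| Place | Treatment of the event |
|---|---|
| Protocol 10.4.1.1 | TESAE: reported after at least one dose |
| Protocol 5.1, SAP 3.1 | Inside the continuous safety span |
| SAP 6 | Post-treatment: TE period 1 ended at 20 to 28 h and TE period 2 has not begun |
| SAP 6.4.2, definitions | Post-treatment AE, not a TEAE; no agent assigned |
| SAP 6.4.2.1, SOC/PT tables | In none of those listed |
| SAP 6.4.2.1, overview | Counted under all AEs, including the rows for seriousness, relatedness and intensity; no post-treatment category |
| SAP 6.4.2.1, listings | Included in the listing of all AEs |
| SAP 6.4.2, per-AE frequencies by agent | Undetermined: worded for AEs, but no attribution rule applies outside a TE period |

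An event 12 h after gadoterate, by contrast, is treatment-emergent in both documents.

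**2. Size of the gap.** Inputs:

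- separation S between injections: 24 h to 15 days (360 h), Protocol 5.1
- TE period length W: 20, 24 or 28 h, from 24 ± 4 h in SAP 6
- safety span: from gadoterate to 24 h after gadobutrol, so S + 24, Protocol 5.1

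Gap = max(0, S − W). Share of the safety span = gap / (S + 24). Only time between the injections is counted as gap.

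| S | Gap, W = 28 h | Gap, W = 24 h | Gap, W = 20 h | Share of span, W = 24 h |
|---|---|---|---|---|
| 24 h | 0 h | 0 h | 4 h | 0/48 = 0% |
| 48 h | 20 h | 24 h | 28 h | 24/72 = 33% |
| 168 h (7 days) | 140 h | 144 h | 148 h | 144/192 = 75% |
| 360 h (15 days) | 332 h | 336 h | 340 h | 336/384 = 87.5% |

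At 15 days the share runs from 332/384 = 86.5% to 340/384 = 88.5% across the three window lengths. Under the protocol's definition the gap is 0 h at every separation. The separations of 48 h and 7 days are illustrations, because the documents give no distribution of intervals.

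**The case against.** The case for leaving the SAP alone has substance.

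- **The protocol partly supports the SAP's window.** Section 9.2.2 monitors TEAEs for 24 h after each agent, section 9.2.5 ties a 24 ± 4 h phone contact to each injection, and tabulation by agent (11.4.2.6) needs an attribution rule that 10.4.1.1 does not give. This stands: the inconsistency lies partly within the protocol. It does not remove the conflict, because 10.4.1.1 is the definition and 5.1 describes a continuous span.
- **Gap events are not hidden.** They are in the all-AE overview, with its rows for seriousness, relatedness and intensity, and in the listings. SAEs in the observation period also go to the sponsor within 24 hours (Protocol 10.4.1.5). This stands. What is missing is a breakdown by term.
- **Most contrast reactions come early.** Protocol 10.4.1.4 says the majority of TEAEs occur within 30 minutes, well inside the window. This stands, and it means that a share of time must not be read as a share of events.
- **Safety is descriptive.** No hypothesis, power or alpha depends on this definition.

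A reader might go further and infer that all events between the injections leave every by-term safety table. The documents do not support that. Events in the first 24 ± 4 h after gadoterate remain TEAEs, the gap almost vanishes at the minimum separation, and the general per-AE frequency sentence in SAP 6.4.2 may or may not take in gap events. A reader might also take shares of the inter-injection interval, such as 140/168 = 83% or 332/360 = 92% (28 h window), as a measure of lost events. They are shares of clock time at chosen separations.

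**Conclusion.** The conflict is real and worth correcting, within limits. It concerns AEs and SAEs that start later than 24 ± 4 h after gadoterate and before gadobutrol. These are TEAEs or TESAEs under Protocol 10.4.1.1 but post-treatment AEs under SAP 6 and 6.4.2, and they have no place in the SOC/PT tables that SAP 6.4.2.1 lists. The time affected runs from 0 to 4 h at 24 h separation to 332 to 340 h at 15 days. The number of events affected cannot be derived from the documents. The conclusion assumes that the TE period closes somewhere between 20 and 28 h and that the SOC/PT tables are those listed. It is a matter of consistency and completeness in the safety output: the events would still be recorded and listed, and the efficacy conclusions are untouched.

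**What to change.** 1. Reconcile the TEAE and TESAE definition across Protocol 10.4.1.1, Protocol 9.2.2 and SAP 6 and 6.4.2, so that one rule applies.
2. Keep the 24-hour windows as the like-for-like comparison of the two agents.
3. Add to SAP 6.4.2.1 a SOC/PT table of post-treatment AEs and SAEs, or of all AEs and SAEs after the first dose, and a post-treatment column in the overview.
4. State how gap events are attributed, and whether they enter the per-AE frequencies by agent in SAP 6.4.2. Extend the post-treatment period to subjects who never reach Study Period 2. SAP 6 leaves their time after the first TE period unclassified, although the medication rule in SAP 6.1.6 covers it.
5. Record the departure from Protocol 10.4.1.1 in SAP section 7.

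The cost is SAP wording, protocol wording where 9.2.2 and 10.4.1.1 are aligned, and a few tables from data already collected. The drawback is that follow-up in the added tables is longer after gadoterate than after gadobutrol. They should carry a note saying so and should not be used to compare agents.

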6.4.2.1 Overview of AEs

The number and percentage of subjects experiencing AEs will be summarized. Overall summary tables will be provided for all AEs, TEAEs and pretreatment AEs with following categories:

- Any such AEs
- Drug-related AEs
- AEs related to procedures required by the protocol
- AEs by intensity (mild, moderate, severe)
- Drug-related AEs by intensity
- Serious AEs (SAEs)
- Drug-related SAEs
- SAEs related to procedures required by the protocol
- AEs leading to discontinuation of study drug
- SAEs leading to discontinuation of study drug
- AEs leading to death.

The overall summary table will also be presented on AEs of subjects only receiving gadoterate but not included in the SAF.

The number and percentage of subjects with TEAEs will be summarized for the following:

- TEAEs and treatment-emergent SAEs (TESAEs) by SOC and PT
- Drug-related TEAEs and TESAEs by SOC and PT
- Nonserious TEAE by SOC and PT
- TEAEs and TESAEs resulting in discontinuation of study drug by SOC and PT
- TEAEs and TESAEs by maximum intensity, SOC, and PT
- Drug-related TEAEs and TESAEs by maximum intensity, SOC, and PT
- TEAEs and TESAEs by worst outcome, SOC, and PT
- Drug-related TEAEs and TESAEs by worst outcome, SOC, and PT

Common TEAEs, TESAEs, drug-related TEAEs, and drug-related TESAEs with frequency $\geq 1\%$ by SOC and PT.

Tables will be sorted alphabetically by SOC and PT.

Subject listings of all AEs as well as subset listings of AEs leading to death and AEs resulting in discontinuation of study drug will be created.

